## Resources Available

The research team assigned to the study for screening, consenting and data collection purposes will be the Research Coordinator who is a RN and three data abstractors that work on post-operative RARP patient follow up. Two members are medical assistants with experience of screening and consenting in research as well as clinical experience in urology.

- Justify the feasibility of recruiting the required number of suitable subjects within the agreed recruitment period. [name] clinical practice sees approximately 900 patients a year in consultation for RARP as treatment for prostate cancer. Approximately 11% will be needed for enrollment.
- There is no additional surgical time needed for this study. The approximate surgical time is 90 minutes.

## Study Procedures

### SUBJECT RECRUITMENT AND SCREENING

Participants for enrollment will be recruited from the clinical practice of [name]. A researcher will screen the patient's medical record specifically looking at diagnostic lab and path reports to verify inclusion/exclusion criteria for potential enrollment. If the patient indicates he would like more information, a qualified researcher will approach the patient, in a private room, to provide an overview of the study.

### CONSENT PROCESS AND DOCUMENTATION

If the patient meets the criteria for enrollment and is interested in participating in the study, a researcher will be notified and the informed consent process will commence. Patients will be informed that their participation in the study is voluntary and the decision to participate in no way will affect their care for prostate cancer. If the patient continues to express interest in the study, a copy of the IRB approved informed consent form will be given to the patient to read. The patient will be able to ask questions and have a sufficient amount of time prior to signing the informed consent document. After signing the informed consent form, a complete and signed copy will be given provided to the patient.

In the unlikely event that a non-English speaking patient meets criteria for enrollment, then IRB Short Form procedures will be initiated.

*Waiver of Written Documentation of Consent or Waiver of Consent We are requesting a HIPAA waiver for the de-identified comparison group that will be looked at*

to compare findings of lymphocele formation. This group whose data already exists will be extracted from our urological outcomes database identified in IRBnet as #237998 which has a waiver of consent in place for data used in research.

N/A

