## Study Design

### RESEARCH DESIGN

The study will be a single institution, single arm prospective trial where by 100 patients will be enrolled.

Participants evaluated and scheduled for a PLND during Robotic Assisted Radical Prostatectomy by [name] who have met the study inclusion criteria and who have also given informed consent will be enrolled. Enrolled participants will have their PLND performed using J-Plasma® for dissection and sealing of lymphatic channels. An abdominal-pelvic ultrasound will be completed at a follow-up period ranging from 4-12 weeks post operatively to determine if a lymphocele is present as this is the standard of care within [name] clinical practice for all patients who undergo a PLND during RARP. The occurrence rate of lymphoceles in this trial group of 100 patients will be compared to retrospective data of 100 patients acquired from the IRB approved Urologic Robotic Surgery Outcomes Registry # 237998 using the same inclusion/exclusion criteria as defined for enrollment in this protocol and from other published data to determine if the occurrence rate has been reduced.

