## Statistical Analysis Plan

### PRIMARY OBJECTIVE ANALYSIS

The primary variable of interest is the incidence of lymphocele formation measured at approximately 8 weeks post-operatively. The incidence of lymphocele formation will be compared between the 100 enrolled “treatment” group and a propensity matched “non-treatment” group that will be established using equal inclusion/exclusion criteria, this retrospective lymphocele data will be retrieved from the Urologic Robotic Surgery Outcomes Registry identified by IRBnet #237998. Additional comparisons of demographic (age, race/ethnicity) and oncological information will be accessed to ensure no differences between the two groups.

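### Registry controls have no calendar window and no check for time trend, so a change over time in the practice's lymphocele rate could pass for, or hide, a J-Plasma effect

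*Combined protocol and SAP*

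**What the plan says.** Research Design describes a single-institution, single-arm trial of 100 patients whose lymphocele rate "will be compared to retrospective data of 100 patients acquired from the IRB approved Urologic Robotic Surgery Outcomes Registry # 237998", chosen with the trial's own eligibility criteria. It then adds a second, undated comparator: "and from other published data to determine if the occurrence rate has been reduced". Randomization is marked not applicable. Study Duration projects a start in February 2016 and one year of enrolment.

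The consent section, in its waiver request for the comparison group, says: "This group whose data already exists will be extracted from our urological outcomes database".

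Primary Objective Analysis calls the control group propensity matched, "that will be established using equal inclusion/exclusion criteria, this retrospective lymphocele data will be retrieved from the Urologic Robotic Surgery Outcomes Registry". It lists no propensity covariates. It continues: "Additional comparisons of demographic (age, race/ethnicity) and oncological information will be accessed to ensure no differences between the two groups".

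The inclusion and exclusion criteria contain no date limit. The variable list under Study Outcome Measures has age at surgery, preoperative Gleason score and PSA, and clinical reports, but not date of surgery. For enrolled patients that date is kept in the master log described under Data De-identification, where the link serves auditing.

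**The concern.** The hypothesis is that J-Plasma reduces lymphoceles. A comparison of a 2016 cohort with earlier patients answers that question only if the rate without the device would have been the same in both periods, given the matched factors. Equal eligibility criteria do not secure this, because the criteria say nothing about time.

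The endpoint is a finding on ultrasound, so it can move for reasons unrelated to the device: extent of dissection, other sealing methods, drainage, scanning equipment, or how readily small collections are reported. A falling background rate would be reported as efficacy, and a rising one would hide a real benefit.

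The only lymphocele rate in the documents, 51%, comes from a paper published in 2011, at least four years before the projected start. Registry patients from that period would be admissible as controls under the plan as written. The undated published data in Research Design carry the same problem.

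**Working it through.** **What the text fixes and what it leaves open**

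- Treated patients: surgery from February 2016, for about a year (Study Duration).
- Controls: retrospective, from the registry, without J-Plasma, under the same eligibility (Research Design, Study Outcome Measures, Primary Objective Analysis); already existing (consent section).
- Earliest or latest control surgery date: not given anywhere.
- Consecutive or most recent cases: not required anywhere.
- Propensity covariates: not listed. Variables named for comparison: age, race/ethnicity, oncological information.
- Time-trend check: none.

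Matching can remove the part of a trend that runs through the matched patient factors, such as a shift in age or oncological risk. It cannot remove changes in technique or detection.

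**The plan's own figure**

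The sample size of 100 cannot be reproduced. Sample Size Determination refers to a 76-patient paper and states no alpha, sidedness, power or target rate. For scale only: at a two-sided 5% level, 100 per group gives 80% power for 51% v about 31.6%, a difference of 51 − 31.6 = 19.4 points.

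**Effect of drift with a useless device**

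Inputs:
- n = 100 per group (Research Design);
- control rate 0.51 (Introduction);
- treated rate 0.51 − d, where d is the fall in the background rate (assumed);
- two-sided 5% pooled z test (assumed; the analysis section names no test);
- matching ignored.

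With x_c and x_t lymphoceles in the control and treated groups and pooled rate p = (x_c + x_t)/200:

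z = [(x_c − x_t)/100] / √[p(1 − p) × 2/100]

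The chance of a false result for J-Plasma is the sum, over all pairs with z > 1.96, of Bin(x_c; 100, 0.51) × Bin(x_t; 100, 0.51 − d).

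For example, 51 v 37 gives p = 0.44 and a standard error of √(0.44 × 0.56 × 0.02) = 0.0702, so z = 0.14/0.0702 = 1.99, which is significant. With 51 v 38, z = 1.85. A gap of 14 patients is enough, so a 10-point drift goes most of the way by itself.

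| Assumed fall d | Treated rate | Chance of false result for J-Plasma |
|---|---|---|
| 0 | 51% | 2.8% |
| 5 points | 46% | 11.4% |
| 10 points | 41% | 31% |
| 15 points | 36% | 58.7% |

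The result does not hinge on 51%. A 10-point fall from an assumed 40% gives 31.6%, and from an assumed 30% gives 37.1%.

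**Drift the other way**

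If the device truly lowers 51% to 31.6%, the exact power is 81%. If the background rate has meanwhile risen by 5 points, the treated group is seen at 36.6% and power falls to 55%.

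**The case against.** A single-arm study with historical controls is an openly stated design choice. Same-practice data, equal eligibility, propensity matching and an ultrasound described as standard for all PLND patients each limit the difference between eras. No drift is documented, 15 points is an extreme case, and 51% is background and a sample-size reference rather than the rate of the actual control group. All of this stands, and it makes the table an illustration, not a forecast. It does not supply a window or a check.

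A reader might infer four stronger things that the documents do not support.

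- *That a rule makes every control precede the trial and bars concurrent controls.* The sentence about existing data sits in a waiver request. It could refer to the time of writing or the time of extraction. Earlier controls are the natural reading, but not a forced one.
- *That surgery date is excluded from the matching.* Its use is unspecified. Age, race/ethnicity and oncological information are given as additional comparisons, not as the propensity covariates.
- *That every change over time counts as a device effect, so that era and device are wholly confounded.* Only the part not explained by the matched covariates does.
- *That a concurrent untreated pool is available.* Resources Available says of about 900 patients a year that "Approximately 11% will be needed for enrollment", but these are consultations, not eligible dissections. The device is commercially available, and nothing says that patients outside the trial would not receive it.

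**Conclusion.** The concern holds in this form: the plan neither limits the age of the controls nor checks whether the lymphocele rate was stable, so an unexplained change over time can be credited to J-Plasma or can hide its effect. Under the assumptions above, the false-positive chance rises from 2.8% to 11%, 31% or 59% for falls of 5, 10 or 15 points. The documents give no time trend, so the actual size is unknown, and the figures depend on the assumed test and on ignoring matching. This is more than a missing detail, because undated controls taken exactly as planned can produce the error. The change should be made; it does not require abandoning the single-arm design.

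**What to change.** 1. In Research Design and Primary Objective Analysis, define the matching pool as consecutive eligible PLND patients of the same practice treated without J-Plasma, going backwards from the first enrolment date within a short calendar window. State the window and fix it before outcome data are seen.
2. List the propensity covariates.
3. Record date or half-year of surgery for both groups. Half-year may be easier to square with the description of the comparison data as de-identified in the consent section and Study Outcome Measures.
4. Show the control lymphocele rate by half-year of surgery, and repeat the primary comparison with only the most recent controls as a sensitivity analysis.
5. Do not put surgery date in the propensity model where all controls precede enrolment. Date would then separate the groups completely, leaving no overlap to match on.
6. If eligible patients who were not enrolled and were treated without J-Plasma in the enrolment year prove to exist, compare with them as a further sensitivity analysis, and extend the waiver wording to cover their records. They may differ from enrolled patients, so they should not replace the main control group.

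The cost is a smaller pool for matching, plus minor changes to the waiver and data-extraction wording. No new trial patients or procedures are needed.

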***Subjects who are not yet adults (infants, children, teenagers)***

N/A

***Cognitively Impaired Adults***

- During screening the health and physical is examined for inclusion and exclusion criteria including information about their past medical and social history. Information from the patient record as well as verbal questioning will be used to identify possible impairment.

***Adults Unable to Consent***

N/A- informed consent by the patient is a requirement for inclusion.

DOCUMENTATION OF INFORMED CONSENT PROCESS

Documentation of the informed consent process is required to establish that the subject was accurately and adequately informed and that no study-related procedures were initiated prior to obtaining informed consent. A research team member will note in the source documentation the consent process, date consent was obtained and that consent was obtained prior to initiating any research procedures.

RANDOMIZATION

N/A

STUDY VISITS

Visit 1: Inclusion and exclusion criteria will be reviewed. If the patient meets criteria, he will be invited to participate in the research study. The patient will be given the informed consent and it will be reviewed with the patient and all questions will be answered.

Visit 2: Day of Surgery. The only non-standard of care item will be with the use of The Bovie J plasma at lymph node dissection and will not be billed to patient.

Visit 3: Patient returns to [name] clinical practice for routine standard of care exam and abdominal ultrasound done at Florida Hospital Celebration.

The following table identifies the procedures in relation to the study timeline.

STUDY VISIT SCHEDULE	Visit 1 Screening/Consent	Visit 2 Surgery day	Visit 3 Abdominal US 8wks post op +/- 4 weeks	
Inclusion and Exclusion Criteria	X			
Informed Consent	X			
RARP with PLND		X		
Abdominal US			X	

#### STUDY DURATION

The study is projected to begin February 2016 once ORA and IRB approval are awarded.

The estimated duration to enroll all study subjects is one year from study approval date.

Participants will remain in the study for 4 months following their robotic assisted radical prostatectomy with pelvic lymph node dissection.

The estimated date for investigators to complete the study and analysis of data July 2017.

#### MATERIALS OF HUMAN ORIGIN: COLLECTION, PREPARATION, HANDLING AND SHIPPING

N/A

### **Study Outcome Measures (Endpoints)**

The primary outcome to be measured will be the incidence of lymphocele formation as diagnosed upon post-operative abdominal ultrasound. The incidence of lymphocele formation in patients undergoing pelvic lymphnode dissection using the JPlasma® will be compared to de-identified retrospective data of lymphocele formation without the use of JPlasma® extracted from [name] urologic outcomes registry identified by IRBnet #237998.

The following data variables and materials will be collected for analysis in this study:

- Age at day of surgery
- Pre-operative Gleason Score
- Pre-operative PSA lab value
- Clinical variables: pathology report from RARP, radiology report from abdominal ultrasound, physician notes, nurses notes.

## Data Management and Quality Plan

### DATA DE-IDENTIFICATION

- Unique identifiers will be generated by the researcher at the time of enrollment. The number will consist of the last two digits of the year enrolled as well as the number to designate the order in which enrollment occurred.  
*Ex: first patient enrolled during 2016 would be designated as patient 16-01*
- Data is linked by the research coordinator creating a master log containing patient Name, DOB, DOS MRN and study ID number.
- This link will be used for auditing purposes.
- The linked study master file will be kept on the FH H: drive in a password protected file.
- Members of the GRI Study team as listed on the Delegation Log will have access to this linked file.
- Data will be stored for a minimum of 7 years after the closure of the study.
- The link will be kept for a minimum of 7 years after study closure.

### DATA CONFIDENTIALITY, STORAGE, AND RETENTION

All electronic data will be stored in the FH H: drive. Only FH employees will have access to this drive. All files with identifiable data will be encrypted with password protection. Only those indicated on the Delegation Log will have access to the data. The study documentation and paperwork will be stored at Florida Hospital Global Robotics Institute in a locked storage closet during the course of the study. After study closure data will be retained for 7 years at Iron Mountain Records Facility. After that period of time, all individual patient study information will be shredded.

### DATA QUALITY

Quality control procedures for this research study include source data verification by randomly selecting 10% of subject records with comparison between the paper case report form (CRF) and the medical record and/or electronic database record of those same data. If errors are common, data will be completely checked prior to data analysis.

### DATA SHARING (OUTSIDE OF FLORIDA HOSPITAL)

If any data is to be shared outside of Florida Hospital a formal request will be made to the ORA and FH legal.

## Sample Size Determination

The primary outcome measure is the incidence of lymphocele after robot assisted pelvic lymph node dissection. A previously published paper by [name] on this topic using a cohort of 76 patients was referred to for sample size determination [3].

## Statistical Analysis Plan

### PRIMARY OBJECTIVE ANALYSIS

The primary variable of interest is the incidence of lymphocele formation measured at approximately 8 weeks post-operatively. The incidence of lymphocele formation will be compared between the 100 enrolled “treatment” group and a propensity matched “non-treatment” group that will be established using equal inclusion/exclusion criteria, this retrospective lymphocele data will be retrieved from the Urologic Robotic Surgery Outcomes Registry identified by IRBnet #237998. Additional comparisons of demographic (age, race/ethnicity) and oncological information will be accessed to ensure no differences between the two groups.

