### **Early Withdrawal of Subjects**

#### INVESTIGATOR WITHDRAWAL OF SUBJECTS

Patients that did not receive a pelvic lymph node dissection at the discretion of the surgeon during their robotic radical prostatectomy will be withdrawn from the study.

Patients that do not return for the abdominal ultrasound post operatively as ordered by the physician will be withdrawn from the study.

If a patient is withdrawn from the study they will be notified via telephone call by GRI Research Staff. After 3 failed attempts by phone a certified letter will be mailed to the patient as the final attempt of notification.

All withdrawn participants will be documented in the regulatory binder.

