#### DATA COLLECTION AND FOLLOW-UP FOR WITHDRAWN SUBJECTS

Patients who request withdrawal prior to the post-operative abdominal ultrasound will not be included in the final analysis as there would be unsuccessful collection of the data necessary to conclude the study's end point. Patients who request to withdraw after the abdominal ultrasound will have their data maintained in the research database up to the

point of withdrawal. This data will be included in subsequent analysis because keeping these patients in the analysis is essential for study validity.

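### Do the withdrawal rules leave the primary comparison of 100 enrolled patients without a usable denominator?

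*Combined protocol and SAP*

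**What the plan says.** **Size of the comparison.** The Research Design section enrols 100 patients and states: "The occurrence rate of lymphoceles in this trial group of 100 patients will be compared to retrospective data of 100 patients acquired from" the outcomes registry. The Primary Objective Analysis repeats the figure ("The incidence of lymphocele formation will be compared between the 100 enrolled") and describes the comparator as a propensity-matched "group that will be established using equal inclusion/exclusion criteria, this retrospective lymphocele data will be retrieved from the Urologic Robotic Surgery Outcomes Registry". The site section calls 100 an estimate. Resources Available says "Approximately 11% will be needed for enrollment", which is 100/900 = 11.1% of a year's consultations.

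**Leaving the study.** Investigator Withdrawal of Subjects removes patients who had no node dissection and adds: "Patients that do not return for the abdominal ultrasound post operatively as ordered by the physician will be withdrawn from the study". Data Collection and Follow-up for Withdrawn Subjects states: "Patients who request withdrawal prior to the post-operative abdominal ultrasound will not be included in the final analysis", because the endpoint data would not have been collected.

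**Outcome and scan.** Study Outcome Measures defines the outcome by the postoperative abdominal ultrasound and lists its radiology report among the variables to be collected. The Primary Objective Analysis says: "The primary variable of interest is the incidence of lymphocele formation measured at approximately 8 weeks post-operatively". Research Design gives a window of 4 to 12 weeks and calls the scan standard of care for everyone in the practice who has a node dissection with the prostatectomy. The visit table gives 8 weeks plus or minus 4. Inclusion criterion 5 asks only that the patient be willing and able to return within 12 weeks. Exclusion criterion 3 covers aborted dissection.

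**Controls.** The waiver paragraph says: "This group whose data already exists will be extracted from our urological outcomes database".

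**The concern.** Taken literally, a comparison on all 100 enrolled and a rule that removes some of them agree only if nobody is lost. The protocol foresees loss: an aborted dissection can be known only at surgery, after consent. The plan does not name an analysis set, mention replacement, or say whether matching comes before or after removal. For patients who simply fail to return, exclusion from the analysis is implied but not stated.

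The second worry is asymmetry. A completed scan is a written condition for treated patients, through the withdrawal rules. For controls only the eligibility criteria carry over, and willingness to return is not a completed scan. If unscanned patients stayed in one group's denominator as if scan-negative, that group's rate would fall with no real difference. In a non-randomized comparison with a single endpoint, funded by the device maker, an open denominator is a fair thing to check.

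**Working it through.** **Reading the sections together**

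1. The outcome exists only if an ultrasound was done (Study Outcome Measures). An unscanned patient therefore has a missing outcome, not a negative one.
2. Patients who ask to leave before the scan are out of the final analysis, for the stated reason that the endpoint was not collected. The same reason covers non-returners, whom the investigator withdraws.
3. No dissection is also an eligibility matter (exclusion 3), and the eligibility criteria apply to controls. On this point the two groups are treated alike.
4. The windows agree: 8 ± 4 weeks is 4 to 12 weeks, approximately 8 weeks is its center, and criterion 5 has the same upper limit. Only a rule for out-of-window scans is absent.

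The analysis set is therefore patients with a dissection and a scan.

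**Inputs.** Control rate 51%, with 15.4% of lymphoceles symptomatic (Introduction); 100 per group (Research Design). Assumed, because the documents give no figure: losses m of 5%, 10% and 20%; treated rates of 31% and 36%; a two-sided 5% pooled two-proportion z test, unpaired, enumerated exactly over both binomials. The plan's 100 cannot be reproduced, since Sample Size Determination cites only a published cohort of 76.

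**A. Rules followed, loss unrelated to outcome.** Treated n = 100(1 − m) = 95, 90, 80. With no device effect (51% in both groups), the chance of a significant result favoring the device is 2.8% at 100 v 100, and 2.4%, 2.6% and 2.6% at 95, 90 and 80 v 100. There is no bias.

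| Power | no loss | 5% | 10% | 20% |
|---|---|---|---|---|
| 51% v 31%, matched controls also lost | 83.1% | 80.2% | 78.8% | 72.6% |
| 51% v 31%, all 100 controls kept | 83.1% | 81.8% | 80.7% | 78.2% |
| 51% v 36%, matched controls also lost | 58.7% | 54.7% | 52.4% | 47.2% |

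**B. Controls scanned selectively.** Suppose symptomatic controls are always scanned and the rest with probability s.

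- Symptomatic share: 0.51 × 0.154 = 0.0785.
- Share scanned: 0.0785 + 0.9215s = 0.908 (s = 0.9) or 0.816 (s = 0.8).
- Rate among scanned: [0.0785 + (0.51 − 0.0785)s] / share scanned = 51.4% or 51.9%.
- False favor for the device: 3.2% or 3.8%, against 2.8%.

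**C. Codings that would do damage.**

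- Unscanned treated patients kept in the 100 as negatives: with no effect the treated rate reads 0.51(1 − m) = 48%, 46%, 41%, and false favor is 6.0%, 11.7%, 32.0%.
- Unscanned controls recorded as negatives, at 5% or 10%: power for 51% v 31% falls from 83.1% to 72.1% or 58.6%, against the device.

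No section prescribes either coding. The first also conflicts with the outcome definition and the withdrawal rule.

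**The case for a change.** The strongest reply is that a natural reading is not a written rule. The plan never says that non-returners leave the analysis or that a control must have been scanned, and it names neither a scan-done field nor a scan date for the registry extract. Willingness to return cannot be checked in existing, de-identified records. If the extract could not tell an unscanned control from a negative one, the loss of power in case C would be real. The choice could also be made after the results are seen, and a sentence or two would settle it.

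Part of this stands: the text is silent on the analysis set, on replacement and on out-of-window scans. But silence on replacement is not a rule against it, and a planned enrolment figure beside withdrawal rules is ordinary protocol writing. The radiology report is on the list of variables, which does not confine it to treated patients, and such a report would normally show whether and when the scan was done. Scanning is described as routine for all such patients, so few controls should lack one. The damaging control scenario depends on a registry structure that the documents do not describe.

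Loss related to outcome could still bias the treated rate. Renaming the analysis set would not cure that, because an unscanned patient's outcome stays unknown under any definition.

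**Conclusion.** No change follows. The reference to 100 enrolled gives the planned size, and the withdrawal rules and the outcome definition determine who can be analyzed: patients with a dissection and an ultrasound. The same condition follows sensibly for controls. On that reading, loss unrelated to outcome gives no bias. Power for 51% v 31% falls by about 3, 4 and 10 percentage points at 5%, 10% and 20% loss if matched controls go too, and no documented power target is breached. Selective scanning of controls adds at most 1 percentage point to the false-favor rate in the cases examined (3.8% against 2.8%).

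This rests on assumed loss rates, assumed treated rates and an assumed unpaired two-sided 5% test, since the plan gives none of these. It also rests on the protocol's statement that the scan was routine. Writing down the analysis set would record what an analyst would do anyway.

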## **Safety Monitoring Plan**

Research and safety data will be reviewed by the PI. This review will take place at regular meetings for every 25 enrolled subjects or every 4 months from the first date of enrollment which ever should occur first. These meetings will be with the research coordinator. All CRF data will be source data verified using a risk-based approach to assure the accuracy of the reported data.

DATA AND SAFETY MONITORING BOARD (DSMB) OR EQUIVALENT

N/A

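### Nothing in the plan stops the registry match from being chosen or repeated with the controls' lymphocele results in view

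*Combined protocol and SAP*

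**What the plan says.** The Research Design section describes a "single arm prospective trial where by 100 patients will be enrolled" with no randomisation. The lymphocele rate "will be compared to retrospective data of 100 patients acquired from the IRB approved Urologic Robotic Surgery Outcomes Registry # 237998", "and from other published data to determine if the occurrence rate has been reduced". The Primary Objective Analysis section describes the comparator differently, as "a propensity matched “non-treatment” group that will be established using equal inclusion/exclusion criteria, this retrospective lymphocele data will be retrieved" from the same registry.

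On the controls' data, Consent Process and Documentation says: "This group whose data already exists will be extracted from our urological outcomes database". Study Outcome Measures confirms that lymphocele formation is among the registry data to be extracted, in de-identified form.

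After the match, the analysis section adds: "Additional comparisons of demographic (age, race/ethnicity) and oncological information will be accessed to ensure no differences between the two groups". It gives no balance threshold and does not limit re-matching.

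Two other sections bear on who might see what. Resources Available lists a research coordinator and "three data abstractors that work on post-operative RARP patient follow up" for screening, consent and data collection. The Safety Monitoring Plan says "Research and safety data will be reviewed by the PI", at meetings with the coordinator after each 25 enrolments or four months, whichever comes first.

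**The concern.** Without randomisation, the choice of controls does the work that allocation would otherwise do, and the control rate is half of the primary comparison. A propensity match protects that comparison if its specification is settled without knowledge of the outcome. Here the outcome is already on file for every candidate. The specification is open, so several matches would be equally defensible, and each would give a somewhat different control rate.

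If the choice among them is made, even without intent, when the rates are visible, the control rate can drift upwards and a reduction can appear where there is none. A genuine reduction would also be harder to defend, because the file would hold no dated record that the controls were fixed first. Masking the people who read the scans would not help, since the question is which patients enter the comparison.

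**Working it through.** **Step 1. What the documents fix and what they leave open.**

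- Outcome known before selection: yes (Consent Process and Documentation; Study Outcome Measures).
- Constraints on the control set: the trial's eligibility criteria and the label of propensity matching (Primary Objective Analysis).
- Not stated: covariates in the score, matching ratio, caliper, algorithm, registry calendar window, balance criterion, or a rule for choosing 100 from a larger eligible pool.
- Not stated: withholding of the lymphocele field, a matcher without access to outcomes, or a locked list.
- De-identification removes names. It does not hide the lymphocele result.

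**Step 2. Is there a figure of the plan's own to reproduce?** No. The Sample Size Determination section refers to a published cohort of 76 and gives no alpha, power or target rate, and the plan names no test. The size of the problem must therefore be illustrated.

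**Step 3. Inputs for the illustration.**

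- From the documents: 100 treated and 100 controls (Research Design); a historical rate of 51% (Introduction).
- Assumed: no device effect, so 51% in both groups; a two-sided 5% test; an eligible pool of M registry patients; K candidate sets of 100 drawn at random from the pool, with the highest-rate set kept.

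Test statistic: z = (p_control − p_treated) / √[2·p̄(1 − p̄)/100], where p̄ is the pooled rate. A reduction is declared if z > 1.96. At p̄ = 0.51 the standard error is √(2 × 0.51 × 0.49/100) = 0.0707, so a difference of about 1.96 × 0.0707 = 0.139, or 13.9 points, is needed.

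**Step 4. Results.** Ranges show the spread between separate simulation runs.

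| Eligible pool M | One set, fixed blind | Best of 3 | Best of 10 |
|---|---|---|---|
| 120 | 2.8% | 4.5–4.8% | 6.6% |
| 200 | 2.8% | 5.7–5.8% | 10.4–10.6% |
| 300 | 2.8% | 6.3% | 12.3% |
| 400 | 2.8–2.9% | 6.4–6.5% | 13.0–13.1% |

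The nominal one-directional error is 2.5%. The 2.8% for a single set reflects the discreteness of the counts.

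With M = 400 the mean control rate moves from 51.0% to 54.7% (best of 3) or 57.6% (best of 10). Those shifts of 3.7 and 6.6 points are 3.7/13.9 = 27% and 6.6/13.9 = 47% of the difference needed for significance.

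**Step 5. Does the random-set model mislead?** Random sets are a simplification of alternative propensity specifications. A smaller simulation (3,000 runs) used actual 1:1 propensity matches on varying subsets of four assumed covariates. With pools of 200 to 400 it gave 6.1–7.0% for 3 specifications and 7.6–9.1% for 5. With a pool of 120 it gave 4.4–5.5%. The two models agree closely. The inflation shrinks as the pool approaches 100, because the candidate sets then overlap heavily.

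**The case against.** The strongest reply is that the documents are silent on sequence and suggest no wrongdoing. Saying that the group will be established and its lymphocele data retrieved is compatible with two separate steps. Propensity matching uses no outcome data, the shared eligibility criteria narrow the choice, and alternative matches could be reported afterwards.

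Much of this stands. A reader might infer any of the following, and the documents support none of them:

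- *Controls and outcomes come out in a single extraction.* No section gives the order.
- *The data abstractors build the match.* Resources Available assigns them screening, consent and data collection; matching is not mentioned, and no section says who does it.
- *The investigator watches a running lymphocele rate.* The Safety Monitoring Plan provides for review of research and safety data. It does not say that a rate is tabulated, or that those present do the matching.
- *The investigator is the operating surgeon.* That may be so, but the surgeon's name has been removed and the identity is not stated.
- *A positive result could not be defended.* That goes too far, for the reasons given in the reply above.

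What the reply does not answer is that compatibility with a sound order does not require one. Propensity matching is outcome-free only if its specification is settled without the outcomes, and here it is unsettled. The balance check, with no threshold and no cap on repeats, leaves re-matching open. Reporting alternatives later shows how sensitive the result is but does not show that the primary match was chosen first.

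**Conclusion.** The point holds in a limited form. The comparator is a propensity-matched registry group whose lymphocele results already exist, and nothing in the documents prevents the match from being chosen or repeated with those results in view. Who builds the match, and in what order data are pulled, is not stated.

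The procedural gap rests on the text alone. Its size does not: pool size, number of candidate sets, the test and the practice of keeping the highest-rate set are all assumptions. Under them the false-reduction rate goes from about 2.5–2.9% to about 5–7% with 120 eligible controls, 6–11% with 200 and 6–13% with 400. The true pool is unknown, so the low end is as possible as the high end. This should be corrected before registry outcomes are pulled, because ignorance of the outcomes cannot be restored afterwards.

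**What to change.** Rewrite the Primary Objective Analysis section as a two-step extraction.

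1. State the registry window, propensity covariates, ratio, caliper and balance criterion in advance. Stating the window matters in its own right: someone who knows the practice's rates by period could choose a window even with individual results hidden. Then pull eligibility and matching variables for all candidates, with the lymphocele result and ultrasound report text withheld. Keep whether a scan was done and its date, so that the 4–12 week window can be applied. If these were withheld too, controls with no usable scan could be locked in and could not be replaced, whereas treated patients who do not return for the scan are withdrawn. Run the match, and any re-matching for balance, at this stage only. Lock and date the list of control IDs.
2. Only then merge lymphocele status for the locked IDs. Report any later match as a sensitivity analysis.

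The cost is revised SAP wording and one extra registry query by existing staff. There are no new patients or visits. The real downside is that the primary match cannot be revised once outcomes are merged, so the balance check must be finished in step 1.
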